The use of DBS in the subthalamic nucleus (STN) and globus pallidus interna (GPi) has been shown to improve symptoms of PD.^{4,9,10,11,12,13,14,15,16,17} Several multicenter, randomized controlled trials conducted in the United States, Europe, and in several other geographies worldwide provide evidence of its effectiveness.^{18,19,20,21,22,23,24} Deep Brain Stimulation Therapy is currently delivered in a continuous fashion (cDBS) where stimulation settings are constant over time and do not adjust to fluctuations in symptoms typically experienced by Parkinson's disease patients during medication On and Off states. During On-medication states the addition of stimulation is thought to contribute to dyskinesias and other side effects experienced by the patient.²⁵ To make DBS more responsive to an individual patient's clinical state, investigators have explored the use of adaptive DBS (aDBS) therapy.

aDBS Therapy, also known as closed-loop DBS (cIDBS), adjusts stimulation in a variable fashion. It relies on a biomarker, or signal of interest (SOI), to adjust stimulation. The SOI must correlate to a patient's clinical state (i.e. severity of disease symptoms), dynamically reflect changes in disease symptoms, be persistent over time, be discernible from background artifacts and be measurable with minimal additional intervention.^{26,27,28,29} Perhaps the most studied SOIs within this context are local field

Medtronic Business Restricted

potentials (LFPs), which represent the transient oscillatory activity of various neuronal populations in the brain.

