6.1.2. Medtronic Investigational DBS System Components

aDBS Feature

[figure not shown]
The intended purpose of the aDBS feature is to automatically adjust stimulation amplitude, within clinician-defined limits, based on changes in a patient's brain state measured using Alpha - Beta LFPs as a signal of interest. Under the assumption that correlations exist between brain state and clinical symptoms and side effects, the goal is to maintain the brain state such that certain clinical symptoms and side effects can be managed. The aDBS feature is investigational for this study and is enabled using a Clinician Programmer System with investigational aDBS software enabled. The ADAPT-PD Trial will study two aDBS modes, Dual and Single Threshold modes. Additional modes will be available on the clinician programmer as part of the aDBS feature but will not be used in the ADAPT-PD Trial.

aDBS Dual Threshold Mode

Dual threshold mode includes both an upper and lower control threshold on the LFP SOI and aDBS makes changes to the stimulation amplitude to attempt to maintain the LFP SOI between the two thresholds. In this scheme, when the LFP SOI is "high", then stimulation is increased, whereas when the LFP SOI is "low" stimulation is decreased to control the LFP SOI. When the patient tailored LFP Alpha - Beta power SOI remains between the upper and lower thresholds, stimulation amplitude is held constant. When the Alpha - Beta power SOI exceeds the upper threshold, stimulation increments. When the Alpha - Beta power SOI dips below the lower threshold, stimulation decrements. This aDBS mode is shown in [Figure 2](#).

Medtronic Business Restricted

[figure not shown]
Figure 2: Dual Threshold aDBS Mode

aDBS Single Threshold Mode

Single threshold mode includes a single control threshold on the LFP SOI and aDBS makes changes to the stimulation amplitude based on the measured LFP and whether it is above or below the threshold. In this scheme, when the LFP SOI is above the threshold, then stimulation is incremented and when the LFP SOI is below the threshold, the stimulation is decremented. This mode has shorter default stimulation ramp up and ramp down durations than dual mode. This aDBS mode is illustrated in [Figure 3](#).

Figure 3: Single Threshold aDBS Mode

Investigational Model B35200 Percept PC INS with aDBS Firmware Enabled

Medtronic Business Restricted

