If the subject does not meet all of the LFP screening inclusion criteria and/or meets the LFP screening exclusion criterion, they will be exited from the study following the process in [Section 9.19](#), including a programming session upload to Medtronic via CDU. No further study-related procedures will be completed, and subjects will be followed according to the center’s standard procedures.

At the end of the visit, the programming session, with BrainSense data included in the JSON session data report, will be uploaded to Medtronic via CDU. The subject may resume taking their normal PD medication.

The subject will be reminded of the use of the PD Home Diary and the use of the PKG Watch.

The subject will leave the visit on their current cDBS settings with BrainSense set to Passive Sensing Only in all groups where BrainSense setup was utilized.

Medtronic Business Restricted

9.8.2. cDBS Baseline Period

The subject will remain on cDBS with BrainSense set to Passive Sensing Only for the duration of the period.

Prior to the scheduled cDBS Baseline visit, the PKG Watch will be given to the subject or mailed to the subject's home. Upon receipt, the subject will put on and activate the PKG Watch. The PKG Watch will be worn on the most affected side for at least 6 consecutive days in the 14 days prior to the scheduled cDBS Baseline visit. After the recording, the subject will return the PKG Watch in the pre-paid mailer or bring it to the site for return at the visit.

The PD Home Diary will also be provided to the subject in advance of the visit and will be completed for at least 3 consecutive days in the 14 days prior to the scheduled cDBS Baseline visit. If possible, the PD Home Diary will be completed at the same time as the PKG Watch is worn.

Some assessments may be completed prior to each scheduled visit. See [Section 9.15](#) for detailed information about the administration of each assessment.

Subjects should be contacted prior to the cDBS Baseline Visit to remind them to complete the required between-visit activities (PKG Watch, PD Home Diary and assessments (if applicable)).

9.8.3. cDBS Baseline Visit

30-45 days after LFP screening

Baseline data will be collected, including the following:

- PDQ-39
- EQ-5D-5L
- VHI (worst condition)
- VHI (best condition)
- Parkinson's Disease Sleep Scale (PDSS-2)
- MDS-UPDRS I (Part A) – trained rater
- MDS-UPDRS Patient Questionnaire (Part IB and II) (best condition)

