Utilizing Signal Test, if the subject no longer meets the LFP screening inclusion criterion, it is allowable to re-assess LFP inclusion criterion, at the investigator's discretion, at the start of the first day of aDBS Setup Visit. If the subject does not meet the inclusion criterion, they will be exited from the study following the process in [Section 9.19](#), including uploading the programming session, with BrainSense data included in the JSON session data report, to Medtronic via CDU. No further study-related procedures will be completed, and subjects will be followed according to the center's standard procedures.

The clinician will set up both aDBS Dual and Single Threshold Modes while the subject is Off PD medication. As part of the Off PD medication aDBS setup, the clinician configures the stimulation

Medtronic Business Restricted

amplitude which is automatically adjusted based on the changes to sensed brain signals. Streaming transition schemes and wrist flexion tasks may be utilized as assessments for each mode. Following the Off PD medication aDBS setup, the clinician will assess the programmed aDBS settings (both Dual and Single Threshold Modes) while the subject is On PD medication.

In cases where only one hemisphere has LFP Alpha - Beta signal which meets the inclusion criterion, the following configurations will be used to set up aDBS.

Dual Threshold (DT) Mode:

If only one hemisphere has LFP Alpha - Beta signal $\geq 1.2\mu\text{Vp}$ when setting up the Dual Threshold mode, the clinician should configure adaptive therapy in both hemispheres, using sensing from the hemisphere with LFP Alpha - Beta signal $\geq 1.2\mu\text{Vp}$.

For example, when utilizing BrainSense Setup, if the Left hemisphere has LFP Alpha - Beta signal $\geq 1.2\mu\text{Vp}$, and the Right hemisphere does not, then proceed with the following:

- Set up Dual Threshold mode in the Left hemisphere with the sensing electrode configuration that has met the LFP Alpha - Beta signal inclusion criterion (Preferably the active cDBS card).
- In the Right hemisphere, at Signal Test, select Left STN/GPi as the sensing configuration.
- Note: the stimulation electrode(s) or cathode(s) in the Right hemisphere is not constrained to a sensing configuration.

Single Threshold (ST) Mode:

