If only one hemisphere has LFP Alpha - Beta signal $\geq 1.2\mu\text{Vp}$ when setting up Single Threshold mode, the clinician should configure adaptive therapy in only that hemisphere with LFP Alpha - Beta signal $\geq 1.2\mu\text{Vp}$.

- cDBS should be setup in the hemisphere with LFP Alpha - Beta signal $< 1.2\mu\text{Vp}$ (set to Passive Sensing, if possible).
- Note: that the stimulation electrode(s) or cathode(s) in the hemisphere set to cDBS is not constrained to a sensing configuration.

If one aDBS mode cannot be set up, the subject should continue with the study using only the mode that can be set up and the subject will not be randomized.

If neither aDBS mode can be set up, the subject will be exited from the study following the process in [Section 9.19](#), including uploading the programming session, with BrainSense data included in the JSON session data report, to Medtronic via CDU. No further study-related procedures will be completed, and subjects will be followed according to the center's standard procedures.

Following each aDBS setup visit day, the programming sessions, with BrainSense data included in the JSON session data report, will be uploaded to Medtronic via CDU.

Once aDBS is set up, and prior to the subject leaving the study center On aDBS, the subject's commercially available Patient Programmer System will be replaced with an investigational-marked Patient Programmer System, and the subject will be given the investigational patient labeling. The

Medtronic Business Restricted

clinician or appropriately delegated study personnel will assist the subject to pair the investigational Patient Programmer System with the INS.

Subjects will be instructed on how to pause aDBS any time they feel like the therapy is not working for them by selecting Pause Adaptive Therapy. This Pause Adaptive Therapy (amplitude last delivered in that group prior to starting aDBS therapy (i.e. the suspend amplitude)) is defined by the clinician as part of the aDBS setup process, following the streaming transition schemes testing and prior to starting adaptive therapy. Subjects will notify the investigator when they pause aDBS to assess the scenario and need for any adjustments.

If the visit occurs over 2 days, the clinician may program the subject to one aDBS mode between visit day 1 and visit day 2.

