13.5.3. Endpoint definition

The secondary endpoint is to decrease energy use as measured by TEED during the aDBS Evaluation Phase as compared with TEED during the cDBS Baseline Phase. The Total TEED will be calculated as a sum of the energy use in the left and right leads. There will be one value per patient for each mode evaluated (eg, cDBS, aDBS Dual Threshold, aDBS Single Threshold).

The reduction in TEED will be calculated as:

$$\text{TEED } \Delta_{\text{aDBS dual threshold mode}} = \text{TEED}_{\text{aDBS dual threshold mode}} - \text{TEED}_{\text{cDBS}}$$

and

$$\text{TEED } \Delta_{\text{aDBS single threshold mode}} = \text{TEED}_{\text{aDBS single threshold mode}} - \text{TEED}_{\text{cDBS}}$$

Computing TEED in cDBS

To compute TEED using the formula in [Section 9.15.2](#) in the cDBS mode, the current drain, pulse-width, frequency, and impedance will be determined from the JSON session data at the cDBS Baseline visit.

Computing TEED in aDBS

To compute TEED using the formula in [Section 9.15.2](#) in an aDBS mode, the average current drain from the JSON session data will be computed using the average stimulation currents from the timeline feature. This will be computed as the average of the currents from the timeline feature using the epochs

Medtronic Business Restricted

that align with the analysis set (e.g., As-Treated analysis set uses the actual aDBS mode as reported from the device). Included days should be in the 14 days prior to the visit. The pulse-width, frequency, and impedance will be determined from the JSON session data at the aDBS Evaluation visit.

Impedance

Leads programmed with monopolar settings will use the electrode unipolar impedance between the case and the active electrode. If 2 cathodes are used (dual monopolar settings), TEED will be calculated for each contact separately, and total TEED will be determined for the lead as the sum of the two TEED. Leads programmed to bipolar will use the impedance between the active electrodes. In case electrode impedance was not collected at cDBS Baseline or aDBS Evaluation Phase, impedance from aDBS Setup would be used.

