7.9.2.3 Endpoint definition

The secondary endpoint is to decrease energy use as measured by TEED during the aDBS Evaluation Phase as compared with TEED during the cDBS Baseline Phase.

TEED is defined as the total energy delivered by an electrical system through the DBS leads over an arbitrary period of time. TEED is determined by the stimulation parameters (e.g., pulse width, frequency, amplitude) and the measured impedance.

The calculation of TEED when using constant voltage is:

$$\text{TEED} = (\text{Voltage}^2 * \text{Frequency} * \text{Pulse width}) / \text{Impedance}$$

The calculation of TEED when using constant current is:

$$\text{TEED} = \text{Current}^2 * \text{Frequency} * \text{Pulse width} * \text{Impedance}$$

The Total TEED will be calculated as a sum of the energy use in the left and right leads. There will be one value per patient for each mode evaluated (eg, cDBS, aDBS Dual Threshold, aDBS Single Threshold).

The reduction in TEED will be calculated as:

$$\text{TEED } \Delta_{\text{aDBS dual threshold mode}} = \text{TEED}_{\text{aDBS dual threshold mode}} - \text{TEED}_{\text{cDBS}}$$

and

$$\text{TEED } \Delta_{\text{aDBS single threshold mode}} = \text{TEED}_{\text{aDBS single threshold mode}} - \text{TEED}_{\text{cDBS}}$$

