7.9.2.3.2 TEED calculation by visit

Computing TEED in cDBS

To compute TEED using the formula above in the cDBS mode, the current drain, pulse-width, frequency, and impedance will be determined from the JSON session data at the cDBS Baseline visit.

Computing TEED in aDBS

To compute TEED using the formula above in an aDBS mode, the average current drain from the JSON session data will be computed using the average stimulation currents from the timeline feature. This will be computed as the average of the currents from the timeline feature using the epochs that align with the analysis set (e.g., As-Treated analysis set uses the actual aDBS mode as reported from the device). Included days should be in the 14 days prior to the visit (ie, Visit 1 or Visit 2). The pulse-width, frequency, and impedance will be determined from the JSON session data at the respective aDBS Evaluation visit (ie, Visit 1 or Visit 2).

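### aDBS energy is computed from the square of the mean current, not the mean of the squared current, which understates aDBS TEED only and favours the secondary hypothesis

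*SAP*

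**What the plan says.** SAP 7.9.2.3 gives two formulas. After the words "The calculation of TEED when using constant current is" it sets TEED to current squared times frequency, pulse width and impedance. Protocol 9.15.2 has the same formula.

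For cDBS, the current is the single value in the device session data at the Baseline visit.

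For aDBS, SAP 7.9.2.3.2 says that "the average current drain from the JSON session data will be computed using the average stimulation currents from the timeline feature", over days in the 14 days before the evaluation visit. Protocol 13.5.3 agrees: "This will be computed as the average of the currents from the timeline feature using the epochs" that match the analysis set. The resulting average is the current that enters the formula.

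The secondary hypotheses (SAP 7.9.2.2) are that mean TEED under aDBS minus cDBS is below zero, for each mode. Each is tested only if the primary hypothesis for that mode passes.

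**The concern.** The formula is quadratic in current, so the order of averaging and squaring matters. The plan averages first.

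The two conditions differ in exactly the feature that makes this matter. Protocol 3.1 describes the comparator: "Deep Brain Stimulation Therapy is currently delivered in a continuous fashion (cDBS) where stimulation settings are constant over time". Protocol 9.8.2 adds, for the baseline period, "The subject will remain on cDBS with BrainSense set to Passive Sensing Only for the duration of the period". Under aDBS the amplitude moves by design; for the single threshold mode Protocol 6.1.2 says that "aDBS makes changes to the stimulation amplitude based on the measured LFP and whether it is above or below the threshold". The calculation is therefore correct for cDBS and too low for aDBS, within a paired comparison that looks for a decrease.

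Nothing planned would reveal the error. The complete-case and as-treated sensitivity analyses (SAP 7.9.2.7) change which subjects or epochs are used, not the formula. Imputation, the Wilcoxon fallback and the poolability models all work on the same TEED values.

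At stake are the estimate of energy saved and, if the true saving is small, the error rate of an alpha-controlled test.

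**Working it through.** **The plan's own figure.** SAP 7.9.2.4: difference 22, SD 35, n = 36, one-sided alpha 0.0125, power at least 90%. Using the noncentral t with 35 degrees of freedom and noncentrality 22/(35/6) = 3.77, power is 0.918, so the figure reproduces. (SD 36, also named in that section, gives 0.902.) For the 35 units expected in single threshold mode, noncentrality is 6 and power is 0.9998.

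**Direction.** For any current I that varies over time,

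mean(I²) = (mean I)² + Var(I).

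The plan uses the first term on the right and omits the second. As a share of true energy on an adaptive lead, the understatement is

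b = Var(I) / [(mean I)² + Var(I)] = CV² / (1 + CV²).

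It is zero only if the current is constant, and it is never negative.

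**Size, by assumption only.** The documents give no limits, so the limits below are assumed, with the mean at their midpoint. Two patterns are shown: current spread uniformly between the limits, Var = (U − L)²/12; and half the time at each limit, Var = (U − L)²/4, which is the most that a midpoint mean allows.

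| Assumed limits | Uniform spread | Half the time at each limit |
|---|---|---|
| 1–3 mA | 0.333/4.333 = 7.7% | 1/5 = 20% |
| 1.5–3 mA | 0.1875/5.25 = 3.6% | 0.5625/5.625 = 10% |
| 2–3 mA | 0.0833/6.333 = 1.3% | 0.25/6.5 = 3.8% |

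**Effect on the reported reduction.** If the true reduction is r and both leads adapt, the plan reports 1 − (1 − r)(1 − b). With r = 20% assumed:

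- 1–3 mA: 1 − 0.8 × 0.923 = 26% (uniform), or 1 − 0.8 × 0.8 = 36% (half at each limit).
- 2–3 mA: 1 − 0.8 × 0.987 = 21%, or 1 − 0.8 × 0.962 = 23%.

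**Effect on the test if there is no true change.** With SD 35, n = 36 and nominal alpha 0.0125, an artefact of 2, 5 or 10 TEED units gives a rejection probability of 2.8%, 7.9% or 27.8%. Which of these applies is unknown, because converting a percentage into units needs the TEED level.

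**Which leads are affected.** When only one hemisphere has a usable signal, Protocol 9.9.1 says for dual threshold mode that "the clinician should configure adaptive therapy in both hemispheres", so both leads carry the bias. For single threshold mode, "cDBS should be setup in the hemisphere with LFP Alpha - Beta signal" below the cut-off, and that lead carries none. The documents do not show in which mode the bias is larger overall.

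**What squaring per epoch would leave.** If a share f of the variance lies between epochs, squaring per epoch leaves (1 − f) × b. For 1–3 mA this is 0% at f = 1, 3.8% or 10% at f = 0.5, and the full 7.7% or 20% at f = 0.

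**The case against.** The strongest reply is about importance. The direction is certain, but every percentage above rests on assumed limits and time patterns. The largest needs half the time at each end of a threefold range, whereas dual threshold mode holds the amplitude constant while the signal lies between its thresholds. Near the planned effect the test would pass anyway. The primary test, safety and projected battery longevity (SAP 7.9.3.9, read from the device) do not use this formula. SAP 7.9.3.11 also lists stimulation limits and minimum and maximum current among the device data that may be summarised, and these could bound the bias.

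A second reply is that the remedy may achieve little. If timeline entries are already interval averages, per-epoch squaring misses the variation within each interval. Single threshold mode, with its shorter default ramps, may have much of its variation there. A sensitivity analysis or a stated caveat would then do.

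Most of the facts in this stand: the size is unknown, the correction may be partial, and the consequence lies in a secondary endpoint. They do not rescue the rule as written. The device summaries are optional and not linked to TEED. Not knowing the size of a one-directional error is a reason to remove what can be removed, since otherwise the reported saving cannot be judged. Per-epoch squaring is never further from delivered energy than the planned calculation.

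**Conclusion.** The concern holds. As written, the plan understates aDBS energy on every lead whose current adapts, leaves cDBS energy correct, and so biases the secondary comparison toward a decrease. This follows from the formula and the stated averaging rule, for stimulation under constant current, which is what the aDBS text describes.

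The size is not determined by the documents. Under the assumed limits it runs from about 1% to 20% of aDBS TEED. If the true decrease is near 22 to 35 units, expect an inflated estimate more than a false positive. If the true decrease is close to zero, the nominal 0.0125 error rate is not protected. The documents do not say whether the planned 22 and 35 units were themselves derived from mean current. This should be fixed, but it does not touch the primary conclusion.

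**What to change.** In SAP 7.9.2.3.2 and Protocol 13.5.3:

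1. Compute TEED for each included timeline epoch, per contact and lead (epoch current squared × frequency × pulse width × impedance). Average over the included epochs, then sum the leads.
2. State the epoch length.
3. State that, if timeline values are themselves interval averages, variation within an epoch is not corrected and aDBS TEED remains a lower bound. A bound from the programmed stimulation limits could be added but is optional.

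The cost is revised wording in both documents, with the approvals that Protocol 15.6 requires for an amendment, and a little more programming on device data already uploaded. No visits or subjects are added, and the sample size stands because its inputs are stated in TEED units. The estimated energy reduction will be somewhat smaller.

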7.9.2.3.3 TEED calculations by electrical stimulation mode

Leads programmed with monopolar settings will use the electrode unipolar impedance between the case and the active electrode. If 2 cathodes are used (dual monopolar settings), TEED will be calculated for each contact separately, and total TEED will be determined for the lead as the sum of the two TEED. Leads programmed to bipolar will use the impedance between the active electrodes. In case electrode impedance was not collected at cDBS Baseline or aDBS Evaluation Phase, impedance from aDBS Setup would be used.

